3.1 Definition of Baseline

3.1.1 Double Blind Period

The baseline value for the DBP is the value captured at the Baseline Visit (week 0). In case an assessment has not been performed at the Week 0 Baseline visit or the Week 0 value is missing or invalid, the value from the last completed pre-IMP assessment will be used as baseline.

The screening visit takes place approx. 6 weeks prior and the randomisation visit approx. 2 weeks prior the baseline visit.

3.1.2 Open-label Extension Period

The baseline value for patients who enter the OLE and who have the first visit of the OLE at the same day of the EoTDBP Visit or up to 7 days after the EoTDBP, clinical assessments performed at the EoTBDP Visit will serve as the baseline value for the OLE. For patients entering OLE >7 days after EoTDBP, the OLE baseline value is the value captured at the dedicated Visit 1E.

3.2 Definition of Periods

The study consists of the following periods:

- Screening Period (4 weeks): Screening Visit (V1) to Randomization Visit (V2)
- Randomization Period (2 weeks): Randomization Visit (V2) to Baseline DB Visit (V3)
- Double-blind Treatment Period (varying: 48 to 72 weeks): Baseline DB Visit (V3) to EoTDB Visit (V24) – Time point to be defined by IMP initiation on V3
- Optional Open-Label Treatment Period (48 weeks): from Baseline OLE Visit (V1E) to EoTOLE (V13E) - Time point to be defined by IMP initiation on V1E

Patients will subsequently after end IMP administration enter:

- Safety Follow-up Period 1 following DB (20 weeks): following the EoTDBP Visit (V24) to Safety Follow-up Visit (V25)
- Safety Follow-up Period 2 following OLE (20 weeks): following the EoTOLE Visit (V13E) to Safety Follow-up Visit (SFU-E)

Due to the late approval of the OLE protocol amendment some participants entering the OLE might have entered the first safety follow-up period prior to entering the OLE, and hence would have two safety follow-up periods.

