1.4 Exploratory Objectives

- To explore the target engagement of Lu AF82422 to α -synuclein
- To explore the target engagement of Lu AF82422 on pathological species of α-synuclein
- To explore the relationship between UMSARS, MRI parameters and NfL
- To explore the efficacy of Lu AF82422 for up to 72 weeks of treatment on clinical scales and biomarkers
- To collect patient experience with impaired functions due to MSA to support the interpretation of change on the UMSARS (Exit Interview subset)
- To collect patient experience with study participation (Study Experience Interview subset)

All during the Double-blind Period (DBP).

• To explore the effect of long-term treatment with Lu AF82422 during the open-label extension (OLE)

2 Study Design

- This is a phase II, interventional, randomized, double-blind, parallel-group, placebocontrolled, multi-centre study of the efficacy (slowing disease progression), safety, and tolerability of Lu AF82422 in patients with MSA. The efficacy of Lu AF82422 is assessed using the UMSARS TS; supportive assessments include evaluation of function, global impression of severity of illness, autonomic symptoms, disability, health-related quality of life, biofluid biomarkers, and imaging.
- The target population for this study is patients with possible or probable MSA, as defined by the 2008 Gilman diagnostic criteria. The study will recruit patients with evidence of parkinsonism (MSA-P) and/or cerebellar syndrome (MSA-C). Patients will be allowed stable treatment for managing their symptoms of MSA during the study.
- The patients [N=60] will be randomized to Lu AF82422 CCI or placebo (2:1) via a centralized randomization system (Interactive Response Technology [IRT]). Two strata variables will be applied to ensure a balanced treatment allocation of Lu AF82422 and placebo:CCI and Region (US/Japan, with a maximum of 25% of patients from Japan).
 - maximum of 25% of patients from Japan).
- The study duration from the Screening Visit to the Safety follow-up Visit is between 70 to 94 weeks for patients not entering the optional OLE period and between 118 to 142 weeks for patients continuing in the OLE. The study includes the following periods:
 - Screening period (4 weeks)
 - Randomization period (2 weeks)
 - Double-blind treatment period (48 weeks up to 72 weeks)
 - Optional OLE treatment period (48 weeks)
 - Safety Follow-up Period (20 weeks; will take place after last investigational medicinal product [IMP] administration)

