4.5 Exploratory Endpoints

4.5.1 Double-Blind Period

Disease progression

• as assessed by longitudinal changes from baseline in the abbreviated UMSARS (aUMSARS) score up to EoTDB

Function

• Changes from baseline to Week 48 in aUMSARS

Autonomic symptoms

• Change from baseline to Week 48 in heart rate, blood pressure, and orthostatic symptoms, as assessed in UMSARS Part III

Disease milestones

- Time to wheelchair use, as assessed by the recording of wheelchair use in the physical examination CRF Form
- Change from baseline to Week 48 in frequency of falls, as assessed by PamSys device
- Change from baseline to Week 48 in gait parameters, as assessed by FeetMe device

MRI biomarkers

- Percentage change from baseline to Week 48 in cerebral blood flow in ROIs; putamen and cerebellum, as measured by arterial spin labelling (ASL) MRI
- Percentage change from baseline to Week 48 in tissue integrity in ROIs; primary ROIs: putamen, cerebellar cortex and white matter; secondary ROIs: caudate nucleus, globus pallidus and middle cerebellar peduncle, as measured by diffusion-tensor imaging (DTI) MRI

Blood/CSF biomarkers

- CSF: Change from baseline up to Week 48 in t-tau and NfL concentrations
- CSF: Concentrations of 'free' and 'total' α-synuclein at baseline and Week 48
- CSF: Changes from baseline up to Week 48 in pathological species of α-synuclein
- Blood: Plasma concentrations of 'free' and 'total' α-synuclein during treatment and safety follow-up

4.5.2 **Open-label Extension Period**

Effect on long-term treatment:

- Change from baseline of the DBP and baseline of the OLE to End-of-Treatment of the OLE (EoTOLE) in UMSARS TS and mUMSARS score
- Change from baseline of the DBP and baseline of the OLE to EoTOLE in CGI-S score
- Change from baseline of the DBP and baseline of the OLE to EoTOLE in PGI-S score
- Change from baseline of the DBP and baseline of the OLE to EoTOLE in SE-ADL score
- Change from baseline of the DBP and baseline of the OLE to EoTOLE in health-related quality of life, as assessed using EQ-5D-5L score
- Percentage change from baseline of the DBP and baseline of the EoTOLE in brain atrophy in ROIs, as measured using vMRI
- Change from baseline of the DBP and baseline of the OLE to EoTOLE in blood NfL concentrations

5 Analysis Sets

The patients will be assigned to analysis sets based on IMP intake and post-baseline assessments of the primary efficacy variable in the Treatment Period.

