24.2 Assigning Data to Visits

Invalid assessments will be assigned AVISTN = 888. If the date of last dose is missing, assessments will be considered valid. If multiple assessments are taken the same day, only the last assessment will be valid. Invalid assessments will not be considered in descriptive statistics or statistical analyses but will be included in listings of safety variables.

Assessments at *unscheduled and withdrawal visits* will be assigned to a target day (AWTARGET) based on days after baseline visit, and to an analysis week (AVISTN = AWTARGET/7). Assessments falling outside a defined visit window will be evaluated and will be deemed invalid (AVISTN = 888) for that specific windowing approach in case no obvious week can be identified.

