24.2.1 UMSARS and additional efficacy COAs

For UMSARS, both a narrow and a broad approach will be applied for assigning observations to a visit: 1) observations will be mapped to the nearest official clinical visit in 4-weeks intervals, independent whether UMSARS originally was scheduled for this visit, and 2)

observations will be mapped to the nearest official UMSARS visit in 12-weeks intervals according to protocol.

Nominal Vis Number (DB-Period)	Nominal Vis Week	Nominal Vis Day	Time Window narrow ¹	Time Window broad ¹
V1 (Screening Visit)	-6	-42	NA	NA
V3 (Baseline Visit)	0	0	-7 to 7	-7 to 7
V5 (WD Visit)	4	28	15 to 42	NA
V7 (WD Visit)	8	56	43 to 69	NA
V9 (planned UMSARS/WD Visit)	12	84	70 to 98	15 to 126
V10 (WD Visit)	16	112	99 to 126	NA
V11 (WD Visit)	20	140	127 to 154	NA
V12 (planned UMSARS/WD Visit)	24	168	155 to 182	127 to 210
V13 (WD Visit)	28	196	183 to 210	NA
V14 (WD Visit)	32	224	211 to 238	NA
V15 (planned UMSARS/WD Visit)	36	252	239 to 266	211 to 294
V16 (WD Visit)	40	280	267 to 294	NA
V17 (WD Visit)	44	308	295 to 322	NA
V18 (planned UMSARS/EoTDBP/WD Visit)	48	336	323 to 350	295 to 378
V19 (EoTDBP/WD Visit)	52	364	351 to 378	NA
V20 (EoTDBP/WD Visit)	56	392	379 to 406	NA
V21 (planned UMSARS/EoTDBP/WD Visit)	60	420	407 to 434	379 to 462
V22 (EoTDBP/WD Visit)	64	448	435 to 462	NA
V23 (EoTDBP/WD Visit)	68	476	463 to 490	NA
V24 (planned UMSARS/EoTDBP Visit)	72	504	491 to 518	463 to 518
Nominal Visit Number (OLE-Period)				
V1E (baseline OLEP Visit) ²	0E	0	-7 to 7	-7 to 7
V2E (WD Visit)	4E	28	15 to 42	NA
V3E (WD Visit)	8E	56	43 to 69	NA
V4E (planned UMSARS/WD Visit)	12E	84	70 to 98	15 to 126
V5E (WD Visit)	16E	112	99 to 126	NA
V6E (WD Visit)	20E	140	127 to 154	NA
V7E (planned UMSARS/WD Visit)	24E	168	155 to 182	127 to 210
V8E (WD Visit)	28E	196	183 to 210	NA
V9E (WD Visit)	32E	224	211 to 238	NA
V10E (planned UMSARS/WD Visit)	36E	252	239 to 266	211 to 294
V11E (WD Visit)	40E	280	267 to 294	NA
V12E (WD Visit)	44E	308	295 to 322	NA
V13E (planned EoTOLE Visit)	48E	336	323 to 350	295 to 350

Panel 16 Visit Windows for UMSARS

All post-baseline visits (except EoT visits) can be converted into a Withdrawal (WD) Visit. ¹ For DBP and OLEP, respectively, the applied narrow window will be continuous (i.e., ± 14 days) to avoid invalid assessments (protocol text ± 3 days). The broad window is set up as continuous as well to match. ² EoTDBP Visit will work as Baseline Visit for the OLEP if done within the acceptable window.

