24.2.3 Blood sampling parameters

For blood sampling for IMP, safety lab (only one performed also at screening), α -synuclein and ADA the following windowing will be applied with the addition of the Visit 6 and the Safety follow-up Visit (SFU).

Nominal Vis Number (DB-Period)	Nominal Vis Week	Nominal Vis Day	Time Window narrow ¹	Time Window broad ¹
V1 (Screening Visit – planned sampling)	-6	-42	NA	NA
V3 (Baseline Visit – planned sampling)	0	0	-7 to 7	-7 to 7
V5 (planned sampling Visit)	4	28	21 to 35	21 to 35
V6 (planned sampling Visit)	6	42	36 to 49	36 to 49
V7 (planned sampling Visit)	8	56	50 to 69	50 to 69
V9 (planned sampling Visit)	12	84	70 to 98	70 to 126
V10 (WD Visit)	16	112	99 to 126	NA
V11 (WD Visit)	20	140	127 to 154	NA
V12 (planned sampling Visit)	24	168	155 to 182	127 to 210
V13 (WD Visit)	28	196	183 to 210	NA
V14 (WD Visit)	32	224	211 to 238	NA
V15 (planned sampling Visit)	36	252	239 to 266	211 to 294
V16 (WD Visit)	40	280	267 to 294	NA
V17 (WD Visit)	44	308	295 to 322	NA
V18 (planned sampling Visit)	48	336	323 to 350	295 to 378
V19 (EoTDBP/WD Visit)	52	364	351 to 378	NA
V20 (EoTDBP/WD Visit)	56	392	379 to 406	NA
V21 (planned sampling Visit)	60	420	407 to 434	379 to 462
V22 (EoTDBP/WD Visit)	64	448	435 to 462	NA
V23 (EoTDBP/WD Visit)	68	476	463 to 490	NA
V24 (planned sampling EoTDBP/WD Visit)	72	504	491 to 518	463 to 518
V25 (planned sampling SFU Visit)	88	616	609 to 623	595 to 630

Panel 18 Visit Windows for Blood Sampling Parameters

Nominal Visit Number (OLE-Period)	Nominal Visit Number (OLF-Period)					
$\frac{1}{2} = \frac{1}{2} = \frac{1}$	0E	0	7 +- 7	7 4 - 7		
VIE (BL OLEP VISIT – planned sampling)	UE	0	-/ 10 /	-/ 10 /		
V2E (WD Visit)	4E	28	15 to 42	NA		
V3E (WD Visit)	8E	56	43 to 69	NA		
V4E (WD Visit)	12E	84	70 to 98	NA		
V5E (WD Visit)	16E	112	99 to 126	NA		
V6E (WD Visit)	20E	140	127 to 154	NA		
V7E (planned sampling Visit)	24E	168	155 to 182	127 to 210		
V8E (WD Visit)	28E	196	183 to 210	NA		
V9E (WD Visit)	32E	224	211 to 238	NA		
V10E (WD Visit)	36E	252	239 to 266	NA		
V11E (WD Visit)	40E	280	267 to 294	NA		
V12E (WD Visit)	44E	308	295 to 322	NA		
V13E (EoTOLE Visit – planned sampling)	48E	336	323 to 350	295 to 350		
SFU-E (planned sampling SFU Visit	64E	448	434 to 462	434 to 462		

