All post-baseline visits (except EoT visits) can be converted into a Withdrawal (WD) Visit. ¹ For DBP and OLEP, respectively, the applied narrow window will be continuous (i.e., ± 14 days) to avoid invalid assessments (protocol text ± 3 days). The broad window is set up to allow additional flexibility. ² EoTDBP Visit will work as Baseline Visit for the OLEP if done within the acceptable window.

Since CSF sampling for IMP, NfL, t-tau and α -synuclein quantification only is planned for Visit 3 (Baseline), Visit 18 and Visit 72, the above broad windowing will only be applied around these visits. The above narrow windowing will be identical. CSF sampling will not be performed in the OLEP.

Blood sampling for NfL will be assessed at Screening Visit and Baseline Visit Pre-IMP and at Visit 9, 12, 15, 18, 24, 1E, 7E and 13E post-IMP, and hence the above broad windowing will only be applied around these visits. Again, the above narrow windowing will be fully applied in addition.

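### The SAP still describes a 48-week open-label extension ending at V13E; the protocol's is 96 weeks ending at V25E, so the end-of-OLE endpoints and OLE visit windows need updating

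*SAP*

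**What the plan says.** **SAP.** Section 3.2 gives the period as "Optional Open-Label Treatment Period (48 weeks): from Baseline OLE Visit (V1E) to EoTOLE (V13E", and section 2 repeats it as "Optional OLE treatment period (48 weeks", with a total study duration of 118 to 142 weeks for patients who enter the OLE. The data-handling rules follow the same schedule:

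- Panels 16 (UMSARS) and 17 (MRI) end with the row "V13E (planned EoTOLE Visit" at 48E, day 336. Narrow and broad windows both close on day 350.
- Panel 18 (blood sampling) has one further row, "SFU-E (planned sampling SFU Visit" at 64E, covering days 434-462.
- Section 24.2.3 lists NfL sampling "at Visit 9, 12, 15, 18, 24, 1E, 7E and 13E post-IMP".
- Appendix IV Table 2 stops at 13E, with follow-up at 64E.

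The OLE efficacy endpoints in section 4.5.2 are tied to the end-of-treatment visit. The first is "Change from baseline of the DBP and baseline of the OLE to End-of-Treatment of the OLE (EoTOLE) in UMSARS TS and mUMSARS score". The other six are CGI-S, PGI-S, SE-ADL, EQ-5D-5L, vMRI and blood NfL.

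**Protocol.** The Synopsis, sections 4.1, 7.1.2 and 9.5.1, and Panel 3 set a 96-week OLE: last dose V24E/92E, end of treatment V25E/96E, follow-up V26E/112E, total duration 166 to 190 weeks. Section 4.1 also lets V13E slip, in exceptional cases, to at most 5 months after V12E.

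**Analysis set.** SAP section 5 bases safety outputs for the extension on the OLES. Sections 16.1.5 and 16.1.6 base the OLE adverse event summaries on the APTS.

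**The concern.** The same endpoint wording means Week 48E under the SAP and Week 96E under the protocol. A programmer following the SAP would report the long-term effect half-way through treatment and would have no defined windows for the second 48 weeks.

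The follow-up window is also misplaced. It lies over a period when patients are still being dosed, so by-visit summaries such as vital signs could show an on-treatment visit as post-treatment follow-up. The real follow-up visit has nowhere to go.

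The analysis-set conflict is a separate matter and would exist with a 48-week OLE too. An APTS denominator includes patients who never received an open-label dose, which lowers OLE incidences.

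**Working it through.** **1. Reproduce the stated durations.** Inputs: screening 4 weeks, randomization 2, double-blind period 48 or 72. Follow-up is 20 weeks after the last dose, which is given 4 weeks before end of treatment, so it adds 16.

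- No OLE: 4 + 2 + 48 + 16 = 70; 4 + 2 + 72 + 16 = 94. Both documents agree.
- OLE of 48 weeks: 70 + 48 = 118; 94 + 48 = 142. This is the SAP figure. Follow-up is at 44 + 20 = 64E.
- OLE of 96 weeks: 70 + 96 = 166; 94 + 96 = 190. This is the protocol figure. Follow-up is at 92 + 20 = 112E.

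Each document is consistent with its own OLE length; the two lengths differ.

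**2. Place the protocol visits in the SAP windows.** Nominal day of visit nE = 28 × (n − 1).

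| Visit | Week | Day |
|---|---|---|
| V12E | 44E | 308 |
| V13E | 48E | 336 |
| V14E | 52E | 364 |
| V17E | 64E | 448 |
| V25E | 96E | 672 |
| V26E (follow-up) | 112E | 784 |

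- Uncovered time after the last on-treatment window: 672 − 350 = 322 days; 322/672 = 0.479.
- V14E to V25E fall on days 364, 392, 420, 448, 476, 504, 532, 560, 588, 616, 644 and 672. Against Panel 18, 11 match nothing. V17E (448 ± 3 = 445-451) lies wholly inside the follow-up window 434-462.
- UMSARS at 60E, 72E, 84E and 96E (days 420, 504, 588, 672) has no row in Panel 16. Blood at 72E and 96E has no on-treatment row in Panel 18.
- The protocol's follow-up visit is 784 − 462 = 322 days past the end of the SAP's follow-up window.

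**3. Delayed V13E.** Assume V12E on its nominal day 308. In Panel 18, a V13E 43 to 125 days later (days 351-433) is in no window, and one 126 to 154 days later (days 434-462) is in the follow-up window. Five calendar months are 150 to 153 days, so the permitted limit is day 458 to 461, inside the follow-up window. Panels 16 and 17 have no row after day 350 for such a visit.

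**4. Windows that continue the SAP's own spacing.**

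- Narrow: nominal day −13 to +14, as in the existing rows (V5E, day 112, is 99-126). V14E becomes 351-378 and V25E 659-686.
- Broad cut-offs at midpoints: (336 + 420)/2 = 378; (420 + 504)/2 = 462; (504 + 588)/2 = 546; (588 + 672)/2 = 630; last 672 + 14 = 686.
- Follow-up: 784 ± 14 = 770-798.

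**5. Exposure bands.** SAP section 10 bands stop at 72 weeks. A completed OLE gives (644 + 28) − 0 + 1 = 673 days = 96.1 weeks by the section 10 formula, and (644 + 28) − (0 + 1) = 671 days = 95.9 weeks by the section 24.6 formula. Both lie beyond the last section 10 band.

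**6. Analysis set.** With the same event count, the APTS percentage equals the OLES percentage multiplied by N(OLES)/N(APTS). The documents do not give that ratio.

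**The case against.** The strongest reply is that the SAP has simply not caught up with the protocol. Its 118-142 weeks match the schedule that the protocol's summary of changes marks as superseded, and its seven-day CGI-S recall (24.1.5) also differs from current protocol section 10.2.1.5. A later SAP or OLE addendum may exist. This stands. It also means that the silence of SAP section 23 on OLE length does not show a deliberate or concealed departure. An outdated SAP must still be updated before it governs the OLE analysis.

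The second reply is that the windowing principles can be extended. For UMSARS, "observations will be mapped to the nearest official clinical visit in 4-weeks intervals"; section 24.2.1 carries its principles to the other scales and to the OLE, section 24.2.2 ties the narrow MRI windows to the Panel 16 visits, and the Panel 17 and 18 footnotes describe the narrow windows as continuous. This also stands: much of the gap is missing rows under a stated principle, and the later data need not be lost. It does not move EoTOLE from V13E or the follow-up window from 64E.

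Some stronger inferences are not supported:

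- *V17E will be reported as follow-up.* It could be. Section 24.2 assigns target days explicitly to unscheduled and withdrawal visits, and section 24.2.1 ranks scheduled visits first. Whether Panel 18 day windows would relabel a scheduled V17E is unclear.
- *Later out-of-window values will be discarded.* The rule that a value "will be deemed invalid (AVISTN = 888) for that specific windowing approach in case no obvious week can be identified" follows the sentence on unscheduled and withdrawal visits and leaves a case-by-case decision. Invalid safety values also stay in listings.
- *C-SSRS and PCS results will be wrong.* Post-baseline C-SSRS is summarised as the worst item over the whole period (16.6), and PCS evaluation uses all available assessments in each period (16.2). A wrong visit label changes neither.
- *Adverse events after 64E drop out.* Sections 16.1.4 and 24.3 end the OLE phase at the final OLE follow-up visit. Only the bracketed visit number is stale.
- *All seven endpoints will have 48E values.* In Panel 3 as extracted, V1E and V13E share a column, and six of the seven measures (all but NfL) carry footnote f, which restricts them to late OLE entrants. MRI also carries footnote h. Whether those restrictions apply at V13E is not clear.

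**Conclusion.** The mismatch is certain on the current text of both documents. The SAP points the seven exploratory end-of-OLE endpoints to Week 48E instead of Week 96E, lacks window rows for 12 scheduled visits (48% of planned OLE days), and centres the follow-up window 784 − 448 = 336 days too early. Mislabelling of V17E is possible, not established. How many patients had a delayed V13E is not given; the day ranges assume V12E on its nominal day. The conflict over the OLE safety set is real, but its size cannot be computed from the documents.

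A reader might infer that the trial's main conclusions are at risk. They are not: OLE efficacy is exploratory, mainly descriptive and without formal testing, and the double-blind analyses, adverse event listings and TEAE phase allocation are unaffected by the window error. This should be fixed before the OLE analysis, unless a later SAP or addendum already does so.

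**What to change.** Before the OLE analysis, amend the SAP, or cite the addendum that does so:

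- **Schedule.** Align sections 2, 3.2, 24.2 and Appendix IV Table 2 with EoTOLE at V25E/96E and follow-up at V26E/112E. Replace the stale visit number in 16.1.4 and 24.3.
- **Narrow windows.** Continue in 28-day steps from V14E 351-378 to V25E 659-686.
- **Broad windows.** UMSARS, CGI-S, PGI-S: V16E 379-462, V19E 463-546, V22E 547-630, V25E 631-686. SE-ADL, EQ-5D-5L and blood including NfL: V19E 463-546, V25E 631-686. vMRI: V25E 631-686.
- **V13E.** State which assessments are collected there, given Panel 3 footnotes f and h, and keep a V13E row (broad 295-378) only for those.
- **Delayed V13E.** Map by nominal visit and show the actual day. Under day-based mapping with the extended narrow windows, days 351-462 would fall to V14E-V17E.
- **Follow-up.** Re-centre on day 784 (770-798).
- **Exposure.** Extend the section 10 OLE bands past 72 weeks, up to >96 to ≤100.
- **Safety set.** Base OLE TEAE summaries on the OLES, as section 5 states.

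The cost is one SAP amendment or OLE addendum and the programming of the extra windows. There is no effect on patients and no change to the double-blind analyses.

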3.3 Definition of Withdrawal

The group of patients who withdrew from treatment at the scheduled visits in the Doubleblind Treatment Period will be described as *withdrawn from study*. This group will also contain randomized patients who withdrew from treatment prior to receiving any IMP and patients who died. The complementary group will be described as *completed study*. Patients who withdraw, except for those who withdraw their consent or died, will be asked to attend a Safety Withdrawal Visit 20 weeks after the last dose of IMP and undergo Safety Follow-Up evaluations.

Participants that drop out of the OLE will also undergo Safety Follow-Up evaluations according to trial procedures.

4 Endpoints

4.1 Primary Endpoint, Double-Blind Period

Disease progression

• as assessed by longitudinal changes from baseline in the Unified Multiple System Atrophy Rating Scale (UMSARS) Part I and Part II Total Score (UMSARS TS) up to EoTDB

